## **9.3. Safety Monitoring Plan**

### **Participants Safety**

- The potential risks to study participants include very rare cardiovascular adverse events including arrhythmia and cardiomyopathy. There is a possibility for a breach of confidentiality.

- The potential benefits to study participants include improved visual clarity, shorter operative time, and less frequent need for increased arthroscopic irrigation pump pressure increases, which may result in less fluid extravasation into the surrounding soft tissue and less post-operative pain and analgesic use.
- Adverse Events (AEs), Serious Adverse Events (SAEs) and Unanticipated Problems (UPs) will be identified during clinical assessments by the principal investigator and medical team and reported to the study's safety monitor for review and the IRB. Protection against Study Risks
- Informed consent will be provided both verbally and in written form to subjects. The consent process informs a volunteer about the study, indicates the participation is voluntary and he/she has the right to stop at any time. Risks are enumerated in the informed consent form and described orally during the consent process.
- The procedures to protect against risks with participation in this study are minimized by a safe, hygienic environment for all medical procedures and an experienced, certified staff performing all procedures. The risk of breach of confidentiality is minimized by securing all study related data and PHI behind encrypted, password protected drives and servers.

#### UTHealth CTRC DSMP Checklist

- Primary and secondary outcome measures
  - o Primary: surgeon-rated visual clarity score (visual analog scale 0 to 10), changes in intra-operative arthroscopic pump pressure
  - o Secondary: mean arterial pressure intra-operatively, total operative time, adverse events intra-operatively or post-operatively
  - o Inclusion: patients 18 years of age or older who are able to provide informed consent and who are to undergo arthroscopic shoulder surgery in the seated upright (beach-chair) position requiring visualization of within the subacromial space.
  - o Exclusion: Are unable to provide informed consent, non-English speaker, have a history of adverse medication reaction to epinephrine, and who are having arthroscopic shoulder surgery that does not require visualization within the subacromial space or performed in the lateral position.
  - o Sample size: Thirty (n=30) subjects recruited from Texas will be sought for each group for a total enrollment of sixty (n=60). This is from a power analysis performed. The minimal clinically significant difference in visual acuity score (0-10) is 2 points, or 20%, as established in a prior study. In order to ensure 80% power at an alpha of 0.05, a minimum of 26 patients are needed in each study group.
- List of participating enrolling clinics or data collection centers
  - o Memorial Hermann Memorial City Medical Center
  - o Memorial Hermann Surgery Center West Houston
  - o Memorial Hermann Orthopedic & Spine Hospital
  - o Memorial Hermann Surgery Center
  - o UT Physicians Orthopedics – Texas Medical Center
  - o UT Physicians Orthopedics – Memorial City
- Projected timeline
  - o Based on historic clinic data for the principal investigator and co-investigators, we anticipate meeting our enrollment target around 12 weeks from opening enrollment. Once enrolled, subjects will be randomized into either the epinephrine or placebo group. Surgeon-rated visual clarity score will be obtained immediately post-operatively.
- Target population distribution (e.g., women, minorities, etc.)
  - o The target population distribution will be the typical patients that the principal investigator and co-investigators schedules and operates on here at the UT Health and Memorial Hermann Health systems. Randomization will ensure that both groups will have similar demographic backgrounds.
- Data acquisition and transmission
  - o Clinical assessments and images will be uploaded and stored on Epic and Centricity as is standard. The recorded assessments and images will be stored for study use for at least six years, with all study related data stored in Redcap.
  - o Demographic data (name, age, gender, weight, race) will be collected from medical records and stored in Redcap.
  - o Surgical data (start and stop times for procedure, type of procedure performed, mean arterial pressure) will be recorded and stored in Redcap.

- Objective clinical data (adverse events) will be collected during the post-operative period with information collected stored in Redcap.
  - Subjective clinical data (surgeon-rated visual clarity score, surgeon-requested increase in arthroscopic irrigation pump pressure) will be recorded and stored in Redcap.
  - Imaging data (none)
- Data entry methods
  - A linking log and data collection form will be used to protect subjects' PHI. All data will be entered and stored in a Redcap project drive to ensure maximal security and anonymity.
- Data analysis plan
  - Demographic variables and diagnostic outcomes will be compared using t-test for continuous variables and chi-square or Fisher exact test for categorical variables. A Mann-Whitney rank sum test will be used to compare median visual clarity scores.
- Quality assurance plan
  - To maintain accuracy, consistency and completeness of data, periodic audits and self-assessments will be conducted. The data will be cross-checked by the study coordinator and the PIs to maintain quality control.
- Reporting mechanisms of AEs/SAEs to the IRB, FDA, and NIDA
  - The principal investigator will report all AEs and SAEs occurring in clinical investigations to the IRB according to the UTHSC-Houston IRB policy. A definition of what constitutes an AE or SAE can be found below in this document as well as within the study protocol.
    - AEs will be compiled and submitted on an annual basis to the IRB. Each AE will require review from the investigator as soon as identified.
    - SAEs will be reviewed by the investigator as soon as identified, and all SAEs will be reported to the IRB within 48 hours of identification.
- Reporting mechanisms of IRB actions to NIDA
  - No drugs are involved in this study, so reporting to the NIDA will not be necessary.
- Report of changes or amendments to the protocol
  - All requested changes or amendments to the protocol will be submitted for IRB approval prior to enacting on any subjects previously or to be enrolled. These amendments will be logged and a comprehensive record of all protocol versions and amendments will be maintained by the investigators.
- Trial stopping rules
  - Up to discretion of CTRC/IRB
- Conflict of interest
  - There are no conflicts of interest to report from any of the involved investigators on the study
- Potential risks and benefits for participants
  - The potential risks to study participants include very rare cardiovascular adverse events including arrhythmia and cardiomyopathy. There is a possibility for a breach of confidentiality.
  - The potential benefits to study participants include improved visual clarity, shorter operative time, and less frequent need for increased arthroscopic irrigation pump pressure increases, which may result in less fluid extravasation into the surrounding soft tissue and less post-operative pain and analgesic use.
- Collecting and reporting of AEs and SAEs
  - Adverse Events (AEs), Serious Adverse Events (SAEs) and Unanticipated Problems (UPs) will be identified during clinical assessments by the principal investigator and medical team and reported to the study's safety DSMB and the IRB for review.
    - An Adverse Event (AE) is defined as any untoward medical occurrence associated with the use of an investigational product in humans and that does not necessarily have a causal relation with the investigational product. AEs can therefore be any unfavorable and unintended sign (including an abnormal laboratory finding), symptom, or disease temporally associated with the use of an investigational procedure or product, whether or not related to the investigational procedure or product.
    - An adverse event is considered "serious" if, in the view of the investigator, it results in any of the following outcomes:
      - Led to death
      - Led to serious deterioration in health of the subject, that either resulted in

- A life-threatening illness or injury, or
  - A permanent impairment of a body structure or function, or
  - In-patient or prolonged hospitalization, or
  - Medical or surgical intervention to prevent life-threatening illness or injury or permanent impairment to a body structure or a body function
  - Led to fetal distress, fetal death or congenital abnormality or birth defect, or
  - Required intervention to prevent permanent impairment or damage, or
  - Other serious events that do not fit the other outcomes, but the event may jeopardize the subject and may require medical or surgical intervention (treatment) to prevent one of the other outcomes.
- Management of SAEs or other study risks
  - Within 48 hours of becoming aware of a SAE, the investigator must complete the SAE report (providing as much information as is immediately available). The investigator must submit this SAE report to the study's safety monitor. The investigator must also report all SAEs to the IRB, as is required by the IRB.
  - Plans for Interim Analysis of efficacy data
  - In conjunction with the listed Safety Monitor patient reports will be sent once specific numbers of patients have been enrolled: 30 patients, 60 patients.
- Responsibility for data and safety monitoring
  - All investigators listed on the study will be responsible for upholding ethical and appropriate procedures and handling of subject data. Internal self-monitoring will be performed by the research team to ensure only data listed in the protocol is collected, and ensure the accuracy of the collected data. The principal investigator will ultimately be responsible for ensuring all safe handling of study related information.
- Frequency of DSM reviews
  - Up to discretion of CTRC/IRB
- Content of DSM report
  - Up to discretion of CTRC/IRB

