### **2. HYPOTHESIS AND OBJECTIVES**

#### **2.1. Purpose/Hypothesis**

**Purpose:** The aim of this study is to investigate the effect of a pre-operative subacromial injection containing epinephrine on the visual clarity during subacromial arthroscopic shoulder surgery.

**Hypothesis:** Pre-operative injection of epinephrine into the subacromial space will result in improved surgeon-rated visual clarity as well as decrease the need for increased arthroscopic irrigation pump pressure throughout the arthroscopic shoulder surgery as compared to injection not containing epinephrine.

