#### **2.2. Primary Objectives**

To evaluate surgeon-rated visual clarity and the need for increased irrigation pump pressure during arthroscopic shoulder surgery.

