### **3. STUDY POPULATION**

#### **3.1. List the number of subjects to be enrolled.**

Thirty (n=30) subjects recruited from Texas will be sought for each group for a total enrollment of sixty (n=60). This is from a power analysis performed. The minimal clinically significant difference in visual acuity score (0-10) is 2 points, or 20%, as established in a prior study [1]. In order to ensure 80% power at an alpha of 0.05, a minimum of 26 patients are needed in each study group.

[1] D. Avery, et al., Arthroscopy 31(1) (2015) 12-8.

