## 11. SAMPLE SIZE AND STATISTICAL METHODS

### 11.1. Determination of Sample Size

Thirty (n=30) subjects recruited from Texas will be sought for each group for a total enrollment of sixty (n=60). This is from a power analysis performed. The minimal clinically significant difference in visual acuity score (0-10) is 2 points, or 20%, as established in a prior study. In order to ensure 80% power at an alpha of 0.05, 26 patients are needed in each study group. Minimal attrition is expected given that there is no routine follow-up necessary.

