### 11.2. Statistical and Analytical Plans

Demographic variables and diagnostic outcomes will be compared using t-test for continuous variables and chi-square or Fisher exact test for categorical variables. A Mann-Whitney rank sum test will be used to compare median visual clarity scores. In the case where a serious medication-related adverse events occurs, we will also start an early analysis to determine the potential causes.

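### Two unranked primary outcomes with no success rule; the only alpha, power and target difference concern the visual score

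*Combined protocol and SAP*

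**What the plan says.** **Outcomes.** The outcome list in the section 9.3 checklist reads "Primary: surgeon-rated visual clarity score (visual analog scale 0 to 10), changes in intra-operative arthroscopic pump pressure". The primary objective in section 2.2 is "To evaluate surgeon-rated visual clarity and the need for increased irrigation pump pressure during arthroscopic shoulder surgery". The hypothesis in section 2.1 is that the epinephrine injection "will result in improved surgeon-rated visual clarity as well as decrease the need for increased arthroscopic irrigation pump pressure". None of the three ranks the outcomes.

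**Sizing.** Section 11.1 states: "The minimal clinically significant difference in visual acuity score (0-10) is 2 points, or 20%, as established in a prior study". Section 3.1 adds: "In order to ensure 80% power at an alpha of 0.05, a minimum of 26 patients are needed in each study group". Enrolment is 30 per group. No target difference, standard deviation (SD), expected rate or power is given for pump pressure.

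**Analysis.** Section 11.2, repeated in the checklist, has two sentences on tests. One is specific: "A Mann-Whitney rank sum test will be used to compare median visual clarity scores". The other is general: "Demographic variables and diagnostic outcomes will be compared using t-test for continuous variables and chi-square or Fisher exact test for categorical variables". Neither carries a significance level, an order or a multiplicity rule.

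**Pump-pressure measure.** Sections 2.1 and 2.2 speak of a need for higher pressure. Section 5.1 and the checklist outcome list speak of changes, which section 5.1 measures from a 35 mmHg start. The checklist text on data acquisition speaks of increases that the surgeon requests.

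**The concern.** With two primaries and no rule, the plan does not say whether a positive trial needs clarity, pump pressure, either or both. That could be settled after the results are seen.

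- If either outcome may carry the claim, two tests at 0.05 exceed the one alpha that the plan states.
- If both are required, the error rate is controlled, but the stated 80% is not the power of the joint objective. That joint power is not stated and cannot be derived from the documents.

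The loose description of pump pressure adds a second choice. A need for, or request for, higher pressure points to a yes/no outcome or a count; a change in mmHg points to a numeric one. The general sentence in section 11.2 gives different tests for continuous and categorical data, so the test for a primary outcome would follow from a definition that is not yet fixed.

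**Working it through.** **1. The plan's own figure.** The stated inputs are a 2-point difference, alpha 0.05, 80% power and 26 per group. No SD is given, so 26 cannot be reproduced directly. Solving backwards with a two-sided test, 26 per group needs an SD of about 2.52 (t-test) or 2.52 to 2.57 (normal approximation: n = 2 × (1.96 + 0.84)² × SD² / 2²). The figure is attainable, and it is a calculation for the visual score only.

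**2. Error if either outcome may carry the claim.** Assumptions: each test two-sided at 0.05, jointly normal statistics, no true effect on either outcome. The plan does not state sidedness or the correlation.

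Uncorrelated tests: 1 − (1 − 0.05)² = 1 − 0.9025 = 9.75%.
Benefit direction only: 1 − (1 − 0.025)² = 1 − 0.9506 = 4.9%.

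For correlated tests, the bivariate normal distribution gives:

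| Correlation | Any false claim | False claim of benefit |
|---|---|---|
| 0 | 9.75% | 4.9% |
| 0.5 | 9.1% | 4.5% |
| 0.8 | 7.8% | 3.9% |
| One test alone | 5% | 2.5% |

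Section 1.2 a says that surgeons may raise pressure when the view is poor, so some correlation is likely.

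**3. Error and power if both must succeed.** A false claim then needs two significant tests, so each can stay at 0.05 with no inflation. Joint power cannot exceed the power for clarity. As an illustration only, if each test had 80% power, joint power would be 0.80 × 0.80 = 64% with uncorrelated tests and about 73% at correlation 0.8. The documents give nothing from which to work out the pump-pressure part.

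**4. Clarity first, then pump pressure.** Clarity is tested at the full 0.05, so its power is unchanged. Pump pressure is tested only after clarity succeeds, so family-wise error stays at 5%, provided each test holds its own level.

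The price falls on pump pressure. Assume SD 2.5, Mann-Whitney for clarity with 30 per group, and pump-pressure power of 84.5% taken alone. The chance of confirming a pump-pressure benefit, over correlations 0 to 0.8, is then:

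- about 71% to 79% if clarity differs by 2 points (at correlation 0: 0.845 × 0.845 = 71%);
- about 27% to 32% if it differs by 1 point;
- at most 5% if it does not differ.

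**5. Test choice if pump pressure is yes/no.** Exact enumeration at 30 per group, with common rates from 10% to 50%, gives uncorrected chi-square a true size of at most about 5.5% (near a rate of 11.5%). Fisher's size is only 0.9% at a 10% rate. Power at illustrative rates:

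| Rates compared | Fisher | Uncorrected chi-square | Loss with Fisher |
|---|---|---|---|
| 50% v 20% | 60% | 69% | 9 points |
| 40% v 10% | 71% | 80% | 9 points |
| 30% v 5% | 63% | 78% | 15 points |

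**The case against.** The strongest reply is that no section says success on either outcome is enough. The hypothesis and the primary objective join the two outcomes, which leans towards requiring both, and on that reading nothing is inflated. The hypothesis is also directional, and false claims of benefit stay below 5% even under an either-outcome rule. Both points stand as limits on the size of the concern. They do not close it: the hypothesis states an expectation rather than a decision rule, the checklist simply lists two outcomes, and 4.9% is still about twice the 2.5% of one two-sided test.

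Four stronger readings are tempting, and the documents do not support them.

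- A reader might infer that the trial runs at a 9.75% error rate. That needs an either-outcome rule, which is nowhere stated.
- A reader might infer that the 80% or the 26 per group is wrong. Neither is shown to be wrong. The power sentence follows directly on the 2-point visual difference and does not purport to cover pump pressure.
- A reader might infer that pump pressure has no test at all. The general sentence in section 11.2 can cover it; what is open is which branch applies.
- A reader might take the checklist item "Plans for Interim Analysis of efficacy data" to mean an added efficacy test at 30 patients. The text beneath it describes only patient reports, so no such test is stated, and the matter is separate from this one.

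It is also fair to say that putting clarity first lowers the standing of an outcome that the sponsor chose to call primary. For that reason the both-required rule is an acceptable alternative.

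**Conclusion.** The gap is real and should be fixed. Two outcomes are primary, one is sized, and no rule says how they combine. The plan as written allows two unadjusted primary tests without saying what a claim requires. The inflation to between 7.8% and 9.75% is conditional on an either-outcome rule, two-sided tests at 0.05 and correlations from 0.8 down to 0. Under a both-required rule it is nil, and what remains is that the 80% must not be read as joint power. That two primaries lack a ranking and a rule rests on the text alone. The SD, correlations, pump-pressure power and event rates used above are assumptions, since the documents give none.

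**What to change.** **Success rule.** In sections 2.1, 2.2, 9.3 and 11.2, state that visual clarity is tested first at two-sided 0.05 and that pump pressure is tested at two-sided 0.05 only if clarity is significant. Clarity is the natural first test because it is the only outcome the trial is sized for. If the sponsor instead intends that both must succeed, say so in the same places and state that the 80% applies to clarity only.

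**Pump pressure.** Before any comparison by group, fix one definition and use it in sections 2.1, 2.2, 5.1, 9.3 (outcome list and data acquisition) and 11.2, with the matching test named. If it is yes/no, choose between chi-square and Fisher in advance. Uncorrected chi-square can slightly exceed its level (about 5.5% at most over the rates examined), while Fisher gives up about 9 to 15 points of power at the illustrative rates.

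**Cost.** A few sentences, no extra patients and no loss of clarity power. The downside of the ordered test is that a pump-pressure benefit cannot be confirmed if clarity is not significant. That could happen if surgeons restore the view by raising the pressure, a practice that section 1.2 a describes as possible.

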## **6. METHODS AND ASSESSMENTS**

### **6.1. Randomization and Blinding**

Simple randomization of enrolled subjects will occur prior to surgical intervention. A certified random number generator will be accessed that will generate a number to assign to the enrolled patient. A research coordinator will bring the randomization envelopes on the day of surgery. Blinding of enrolled subjects will be performed to prevent bias from occurring based on patient expectations of the procedure. To reduce recall bias, group allocation will be kept concealed from the investigator until the completion of visual clarity scoring at the conclusion of each surgical procedure.

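### Does the checklist item on interim efficacy analysis, answered only by reports at 30 and 60 patients, leave the 0.05 error rate unprotected?

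*Combined protocol and SAP*

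**What the plan says.** The item sits in the UTHealth CTRC DSMP Checklist within section 9.3 (Safety Monitoring Plan). Its heading reads "Plans for Interim Analysis of efficacy data". The whole answer is that, in conjunction with the Safety Monitor, "patient reports will be sent once specific numbers of patients have been enrolled: 30 patients, 60 patients".

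Two other checklist items bear on it. The item on stopping rules is answered "Up to discretion of CTRC/IRB", and "Content of DSM report" receives the same answer.

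The analysis itself is in section 11.2: "A Mann-Whitney rank sum test will be used to compare median visual clarity scores". That section gives no interim efficacy test and no division of alpha. The one early analysis it mentions follows a serious medication-related adverse event, and its purpose is to look for causes. Section 3.1 states the design error rate: "In order to ensure 80% power at an alpha of 0.05, a minimum of 26 patients are needed in each study group". Section 11.1 repeats it.

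On blinding, section 6.1 says that "group allocation will be kept concealed from the investigator until the completion of visual clarity scoring at the conclusion of each surgical procedure".

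**The concern.** The heading speaks of efficacy data, and the first report falls half-way through enrolment. The document does not say what that report contains, whether it is split by group, or whether a test is run. With report content and stopping left to discretion, one can imagine a between-group test at 30 patients, a second at 60, and success claimed on either. The stated 0.05 would then no longer be the true error rate.

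There is a second worry. Visual clarity is the surgeon's own rating on a 0 to 10 scale. A half-way result by group, if it reached surgeons who still had patients to rate, could colour the remaining scores.

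**Working it through.** **Inputs.** Alpha is 0.05 (sections 3.1 and 11.1). Sidedness is not stated; two-sided is assumed. Reports are at 30 and 60 enrolled (section 9.3). Section 4 has clarity scored immediately after surgery, so 30 enrolled is about 30 with the outcome. The information fraction is therefore 30/60 = 0.5.

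**The plan's own figure.** With one test, at the end, the type I error for visual clarity is 0.05 by construction. The 26 per group cannot be reproduced, because the document gives no SD. By the normal approximation it corresponds to an SD of about 2.57: 2 × 2.57² × (1.960 + 0.842)² / 2² = 25.9, rounded up to 26. This does not affect the present question, since the type I error does not depend on the SD.

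**The feared case.** Under no difference, the test statistics at 30 and 60 are approximately bivariate normal with correlation √0.5 = 0.7071. The overall error is

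P(|Z₁| > 1.96 or |Z₂| > 1.96) = 0.05 + 0.05 − P(both) = 0.10 − 0.0169 = 0.0831.

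- Simulating the Mann-Whitney test at 15 v 15 and then 30 v 30, with assumed scores (mean 6.5, SD 1.5 or 2.57), gives 0.079 to 0.084 depending on the version of the test. A single look gives 0.048 to 0.050.
- Other information fractions give 0.0863 at 0.4, 0.0796 at 0.6, and 0.0804 if the final analysis is at 52 patients (30/52).
- With p < 0.001 required at 30 and 0.05 at the end, the overall error is 0.0502.
- With no efficacy test at 30, it stays at 0.05.

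The 0.083 is not a ceiling. Section 9.3 lists two primary outcomes. If they were independent and each tested at both looks, the error would be 1 − (1 − 0.0831)² = 0.159. But two independent outcomes tested once already give 1 − 0.95² = 0.0975, and that part has nothing to do with interim looks.

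**What the 0.083 requires, set against the text.**

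1. Efficacy data at 30 patients split by group. The answer speaks only of patient reports sent with the Safety Monitor.
2. A significance test on them at 0.05. Section 11.2 has one comparison of clarity scores and no interim test.
3. A rule that p < 0.05 at 30 counts as success. There is none anywhere. The stopping item hands discretion to the CTRC/IRB and does not mention efficacy.

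None of the three steps is in the plan. The report at 60 coincides with full enrolment, so it is not an interim look. If the CTRC/IRB halted the trial for a reason unconnected with the efficacy results, a single test on the patients to hand would still be one test at 0.05.

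**The case for a change.** The strongest case for a change is that the only words describing the purpose of the item name efficacy, and nothing excludes a comparison at 30 patients. The outcome is subjective, and a sentence of clarification would cost nothing. Part of this stands: the heading and the answer do not match, and the arithmetic is right for the case it describes.

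The inference from heading to plan is weak, however. The heading belongs to a standard form that also asks about reporting to the FDA and NIDA, which has little to do with this trial. What the investigators wrote is the answer, and that describes sending reports to a safety monitor. An argument that nothing forbids a test could be made against almost any protocol. There is also little reason to claim success early: section 4 expects enrolment to take about 12 weeks, so 30 patients would come at about week 6 if accrual is even.

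The concern about biased ratings does not depend on the report. Section 6.1 guarantees concealment only until each case is scored, and section 8.5 lets patients learn their group after that. A surgeon could build up an impression of results by group with no report at all. That is a separate question about blinding. Who receives the report cannot be settled from the available text, because the answer refers to a listed Safety Monitor and the list may be on a page that is not public.

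A strict remedy could also do harm. Limiting the 30-patient report to adverse events would keep intra-operative mean arterial pressure from the monitor, although the named risk is cardiovascular. Forbidding any comparison until 60 patients are scored would leave no route to analysis if enrolment closed with fewer.

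**Conclusion.** The concern does not call for a change. Followed as written, the plan makes a single comparison of visual clarity at 0.05, and inflation from repeated looks is zero. The figure of 0.083 is correct for two unadjusted two-sided tests on one outcome at half and full information, but it needs three steps that the document does not contain.

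This rests on reading the 30-patient report as safety reporting, which is the natural reading of the answer and agrees with section 11.2. What remains is an imprecise answer to a form prompt, a gap that analysts fill sensibly by running the one planned test. The conclusion would differ only if an efficacy comparison at 30 patients were actually intended, and the documents give no sign of that beyond the heading.
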